8.1. Morphology and function

CMR provides the reference standard assessment of left and right ventricular morphology and function, with improved accuracy and reproducibility over transthoracic echocardiography (TTE)⁸. Specific indices such as LVEF are widely used to inform decisions on pharmacological and device therapy, yet the use of CMR to assess these parameters has not been validated. Whether specific parameters of cardiac morphology or function predict clinical outcome or the benefit from revascularisation with PCI in this population is also unknown.

8.1.1. Global parameters

- LV end diastolic volume*
- LV end systolic volume*
- LV stroke volume*
- LV ejection fraction
- RV end diastolic volume*
- RV end systolic volume*
- RV stroke volume*
- RV ejection fraction
- Left atrial volume*
- Right atrial volume*
- LV mass*
- LV scar percentage
- LV scar mass*

8.1.2. Segmental parameters (AHA 17-segment model)

- End diastolic wall thickness
- End systolic wall thickness
- Wall thickening
- Wall motion scoring (visual likert scale)
- Scar transmurality (visual)
- Scar burden (quantitative)
 - full width half max (FWHM) (primary) and five standard deviation (5SD) method (exploratory)
 - o bright blood LGE method (primary) and dark blood LGE method (exploratory)

8.1.3. Exploratory analyses in subsets

- Presence of inducible ischaemia (visual, semi-quantitative, and quantitative analysis, depending on source data availability)
- LV strain
- Extracellular volume
- Quantitative perfusion
- Low-dose dobutamine stress
- Scar texture analysis
- LV geometry, perfusion and scar pattern AI analysis

8.2. Scar burden and clinical outcomes

A secondary analysis of the relationship between the number of LV segments with significant scar (defined at exploratory thresholds of \leq 25%, <50%, <75% and 75-100% transmural extent), number of non-viable segments, number of segments with normal function, global LV scar burden (%), scar mass (g) and the number of viable, non-revascularised segments (\leq 25 and \leq 50%) will be performed with the same statistical methods as above.

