4.2. Imaging processing

All viability studies will be analysed by one of two dedicated core laboratories: the King's College London Imaging Sciences CMR core laboratory (led by [name]) and the King's Health Partners Stress Echo core laboratory (led by [name]). Analyses will be performed by trained readers blinded to trial-group assignment and any other clinical data. Viability will be analysed on a segmental basis, using the AHA 17-segment model, excluding segment 17 (the left ventricular apex) as it is incompletely imaged on DSE and not included in CMR quantification. Transthoracic echocardiograms were analysed by the Guy's and St Thomas' echocardiography core laboratory with readers also blinded to the temporal sequence of echocardiograms.

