5.2. CMR - segmental scar transmurality

Segmental scar transmurality is assessed visually on an ordinal scale as 0%, 1-25%, 26-50%, 51-75% and 76-100% of the segmental extent LGE. For trial inclusion, viability was adjudicated according to local protocols, with a recommendation that dysfunctional segments with \leq 25% transmurality be considered viable, \geq 50% non-viable and 25-50% based on local expert opinion. For core-laboratory adjudication, segmental viability was defined as a scar transmurality \leq 25% in a segment which is dysfunctional at rest[2,7,8]. Sensitivity analyses will also be performed using a cut-off of \leq 50%.

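### Viability Study SAP 8.2 sets three of its four exploratory cuts for segments with significant scar as upper limits, so scar-free segments count as scarred and those counts do not measure scar

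*Protocol*

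**What the plan says.** The Viability Study SAP, section 8.2, plans "A secondary analysis of the relationship between the number of LV segments with significant scar" and clinical outcome. The cuts are at most 25%, then "<50%, <75% and 75-100% transmural extent". The same sentence lists further exposures: non-viable segments, normally functioning segments, global scar percentage, scar mass, and viable non-revascularised segments, the last defined at up to 25% and up to 50%. All of this "will be performed with the same statistical methods as above". In section 7.1 that means Cox models with the segment count as a linear effect, followed by a model with its interaction with assigned treatment.

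Section 5.2 gives the measurement scale: "Segmental scar transmurality is assessed visually on an ordinal scale as 0%, 1-25%, 26-50%, 51-75% and 76-100% of the segmental extent LGE". It also gives the meaning of the 25% limit: "For core-laboratory adjudication, segmental viability was defined as a scar transmurality" of at most 25% in a segment that is dysfunctional at rest, with at most 50% as a sensitivity cut. Section 4.2 sets the number of segments at 16, "using the AHA 17-segment model, excluding segment 17 (the left ventricular apex").

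**The concern.** A count of scarred segments needs a lower limit on scar. Three of the four definitions have only an upper limit, so they take in segments with no enhancement at all. Two of those limits, 25% and 50%, are essentially the ones that the SAP uses for viable tissue, both in 5.2 and later in the same sentence of 8.2. Only the 75-100% definition picks out heavily scarred segments.

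At stake is how a set of exploratory results would be read. A hazard ratio labelled as the effect per scarred segment would, at three cuts, describe segments below the cut. It could be reported as protective while the fourth cut and the global scar measures show harm. The direction of any difference in the PCI effect by scar extent would be misread in the same way.

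**Working it through.** The plan states no figure for this analysis, so there is none to reproduce. The check maps the cuts onto the scale and then follows the algebra.

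**Step 1: the cuts of 8.2 on the scale of 5.2**

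| Cut in 8.2 | 0% | 1-25% | 26-50% | 51-75% | 76-100% |
|---|---|---|---|---|---|
| at most 25% | all | all | none | none | none |
| <50% | all | all | split at 50 | none | none |
| <75% | all | all | all | split at 75 | none |
| 75-100% | none | none | none | split at 75 | all |

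The 0% category is wholly inside the first three definitions. A patient with no scar scores 16 of 16 on each of them and 0 of 16 on the fourth.

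**Step 2: the algebra**

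Let S be the number of segments beyond a cut and L the number below it. With all 16 segments scored, L = 16 - S.

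- Without interaction, b·S = 16b - b·L. The constant 16b is absorbed into the baseline hazard. The coefficient of L is -b and its hazard ratio is 1/HR(S). Adjustment for other covariates does not change this.
- With treatment T, the terms b1·S + b2·T + b3·S·T become -b1·L + (b2 + 16·b3)·T - b3·L·T, plus a constant. The interaction coefficient changes sign.
- The model is only reparametrised, so the likelihood and the p-values for the count and for the interaction are the same.

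The text itself supplies an example. The <75% and 75-100% definitions are exact complements. Read cumulatively, they must give reciprocal hazard ratios under the same label of significant scar.

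**Step 3: a worked patient (assumed, for illustration)**

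Take 10 segments at 0-25%, 2 at 26-50%, 2 at 51-75% and 2 at 76-100%, with the cuts mapped to whole categories.

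- As written: 10, 10 + 2 = 12, 12 + 2 = 14, and 2.
- Lower bounds: above 25%, 16 - 10 = 6; above 50%, 16 - 12 = 4; above 75%, 16 - 14 = 2.

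If the true hazard ratio per scarred segment were 1.10 (assumed), the mirror-image count would return 1/1.10 = 0.91.

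**Step 4: simulated illustration**

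Assumptions: 491 patients, 16 segments, three category mixes, a true hazard ratio of 1.02 per 1% of global scar, and 60 replicates per mix. None of these comes from the documents except 491 (the CMR number in 4.1) and 16.

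| Count | HR per segment as written | HR with lower bound |
|---|---|---|
| 25% cut | 0.93-0.94 | 1.07-1.08 |
| 50% cut | 0.92 | 1.08-1.09 |
| 75% cut | 0.91-0.92 | 1.09-1.10 |

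Scar was simulated as harmful. Every replicate gave a hazard ratio below 1 as written and above 1 with lower bounds. The sizes depend on the assumptions; the reversal in Step 2 does not.

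**Step 5: two other readings**

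- *0% segments tacitly excluded* (1-25, 1-50, 1-75). The simulated hazard ratios lie between 0.97 and 1.03, with a sign that depends on the mix.
- *Ascending bands* (up to 25, 25 to 50, 50 to 75, 75 to 100). The worked patient scores 10, 2, 2, 2. The first band still contains scar-free segments, and the middle two leave out the most heavily scarred ones.

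On either reading the counts are no longer mirror images, but the first three still do not count significantly scarred segments.

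**The case against.** The strongest reply is that the text is ambiguous rather than shown to reverse the sign. The list ends in a band, which suggests bands throughout. The word scar might be taken to exclude the 0% category, which has its own place in 5.2. The exact reciprocal needs the literal cumulative reading with every segment scored. This stands, and the reversal is therefore stated only for that reading. Neither alternative rescues the definition, and 8.2 specifies neither.

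It is also fair that the reciprocal is a reparametrisation: no p-value or interaction test changes. Sections 2 and 5.2 make the expected direction plain, so a careful author would probably notice the conflict.

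A reader might infer that the scar-outcome association as a whole comes out with the wrong sign. The documents do not support that. The 75-100% count, global scar percentage, scar mass and the non-viable segment count, all named in the same sentence, keep their direction.

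Inequality signs were damaged in places when the PDF was read, so an extraction error is conceivable. It is unlikely here: three consecutive signs agree, and a greater-or-equal sign is read correctly in 5.2.

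The mismatch with the category borders is small. It concerns only the exact values 50 and 75, and it is a reason to align the cuts, not a separate fault.

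**Conclusion.** The definition is wrong as written, within a narrow scope. Three exploratory, CMR-only counts are labelled significant scar but include scar-free segments, and they contradict both the viability cut in 5.2 and the 75-100% definition beside them. On the literal cumulative reading with 16 scored segments, their hazard ratios and interaction coefficients are the exact reciprocal or negative of those for scar, with unchanged p-values. If some segments are unscored, or another reading is used, the mirror is not exact, but the counts still do not measure what they are named for.

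A reader might infer that this touches the trial's conclusions or every CMR patient. It does not reach the primary endpoint analysis, the viability interaction in 7.1 or the ejection-fraction analyses in 7.2. The 491 patients assessed with CMR are an upper bound, because section 6.4 excludes those whose viability studies are unavailable or unsuitable. The hazard ratios above are illustrations on assumed inputs, not predictions.

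**What to change.** In section 8.2, replace the four cuts with lower bounds that fall on the categories of 5.2: for example, the number of segments with transmurality >25%, >50% and >75%. The authors should confirm which cuts they intend, since the text does not settle it, and record the choice before the scar-outcome results are seen. If bands or counts of preserved segments were meant, name them as such. The change is one line of SAP wording. It needs no new data and no new image reading, because these cuts can be formed directly from the recorded ordinal scale.

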8.3. Visual vs. quantitative scar burden

The extent of myocardial scar burden will be compared between visual and quantitative analysis and FWHM and +/- 5SD data using paired T-tests or the Wilcoxon signed-rank test, depending on the normality of the data.

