4.1. Sample size

In REVIVED-BCIS2 all patients underwent viability imaging prior to randomisation; at least four viable segments which could be revascularised by PCI were required for inclusion. Of the 700 patients enrolled, viability was assessed with CMR in 491 and DSE in 187. Primary outcome data are available for 99.1% of patients. Serial echocardiographic data are available for a subset of these patients.

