8.4. Segmental LV function

Improvement in segmental function will be defined as an improvement in wall motion score ≥1 grade at follow-up. The frequency of functional recovery will be compared between segments based on scar transmurality/scar burden across time points using a repeated measures ANOVA to adjust for repeated measures within the same patient and over three time points of baseline, six months and one year. An unadjusted Cox regression model will be used to test for an interaction between scar transmurality/scar burden and the provision of revascularisation and the likelihood of functional recovery, adjusted for baseline segmental wall motion. Two models will be used for revascularisation; the first where all segments will be considered revascularised in patients who were assigned to PCI, the second where only segments where a territory was documented as having been successfully revascularised in the eCRF, with the attribution of segments based on the standard American Heart

^{*}indexed to body surface area

Association 17-segment model adjusted for dominance of the circumflex or right coronary artery ⁹. Equivalent analyses will also be performed with scar transmurality/scar burden substituted for end diastolic wall thickness/end systolic wall thickness, as well as for different thresholds of LGE for viability (≤50% and ≤ 75%) and where scar burden is treated as a continuous variable. Receiver-operator characteristic curve analysis will be used to examine diagnostic utility, with Youden's index used to calculate the LGE threshold for optimum sensitivity and specificity to predict functional recovery. DeLong's method will be used to compare ROC curves for the prediction of recovery between the FWHM and 5SD methods of defining regions of myocardial scar.

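### Scar-measurement methods are compared only by tests of average difference, which do not show how far two readings of the same scar differ

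*Protocol*

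**What the plan says.** Viability Study SAP section 8.3 consists of one sentence. It states that "The extent of myocardial scar burden will be compared between visual and quantitative analysis and FWHM and +/- 5SD data", and the method is "using paired T-tests or the Wilcoxon signed-rank test, depending on the normality of the data". It gives no acceptable difference, no agreement measure and no unit of analysis.

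Other sections bear on it:

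- Section 5.2 gives the visual scale: "Segmental scar transmurality is assessed visually on an ordinal scale as 0%, 1-25%, 26-50%, 51-75% and 76-100" per cent. It sets the core-laboratory viability cut-off at 25% or less on that visual transmurality scale.
- Section 8.1.2 lists visual transmurality and quantitative scar burden as separate segmental parameters. FWHM is the primary quantitative method and 5SD is exploratory.
- Section 8.4 adds that "DeLong's method will be used to compare ROC curves for the prediction of recovery between the FWHM and 5SD methods".
- Section 8.5 applies a 25% criterion to median scar burden in a vascular territory and calls it the trial-defined viability criterion.
- Section 4.1 gives the numbers: "Of the 700 patients enrolled, viability was assessed with CMR in 491 and DSE in 187".

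**The concern.** When two methods read the same scar in the same patient, the most useful result is usually the size of the disagreement in an individual. The paired t-test has a null of zero mean difference. The signed-rank test has a null of differences symmetric about zero. Neither uses the spread of the differences except as noise, so large errors of opposite sign cancel, while a small constant offset becomes significant once there are enough pairs.

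Individual agreement matters in this plan because the 25% cut-off is defined on visual transmurality in section 5.2 and applied to scar burden in section 8.5. Whether a segment or territory falls on the same side of 25% under both readings cannot be learned from a mean difference.

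There is also a question of scale. Visual reading gives five ordinal grades and quantitative reading gives a percentage. Section 8.3 does not say how a grade becomes a number that can be paired with that percentage.

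**Working it through.** Section 8.3 states no sample size, SD, bias or tolerance, so there is no figure of the plan's own to reproduce. The check is of how the named tests behave.

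**Inputs.** The upper bound on patient-level pairs is 491 (section 4.1). The analysable number is not given, and section 6.4 excludes unavailable or unsuitable studies, so a range of 100 to 491 is used. Two-sided alpha of 0.05 is assumed. The bias b and the SD s of the paired differences, in scar percentage points, are assumed. Pairs are taken as independent.

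**Formulas.** Limits of agreement = b ± 1.96 s. P(significant) for the paired t-test comes from the noncentral t distribution with n − 1 degrees of freedom and noncentrality b√n / s.

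**Wide disagreement.** For limits of ±20, s = 20 / 1.96 = 10.2. With b = 0 the noncentrality is 0, so P(significant) is 5% at every n. A simulation of the Wilcoxon test (1,500 runs) gave 4.9% at n = 200 and 5.0% at n = 491. In the extreme case of 490 pairs, half differing by +20 and half by −20, p = 1.0 on both tests.

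**Close agreement with a small offset.** With b = 0.5 and s = 2, the limits are 0.5 ± 3.92, or −3.4 to +4.4.

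| n | Noncentrality 0.5√n / 2 | P(significant), t-test |
|---|---|---|
| 100 | 2.50 | 70% |
| 200 | 3.54 | 94% |
| 491 | 5.54 | >99% |

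Simulated Wilcoxon rejection was 93% at n = 200 and 100% at n = 491.

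**How conditional this is.** With s = 10.2 and some bias:

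| Bias | n = 100 | n = 491 |
|---|---|---|
| 0.5 | 8% | 19% |
| 1 | 16% | 58% |
| 2 | 49% | 99% |

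With s = 2 and b = 0, P(significant) is only 5%. The bias detectable with 80% power is (1.96 + 0.84) s / √n. At n = 491 that is 2.80 × 2 / 22.16 = 0.25 points for s = 2, and 2.80 × 10.2 / 22.16 = 1.29 points for s = 10.2.

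**Scale of the visual reading.** If grades are turned into numbers, the choice of number matters. The midpoints of the four non-zero bands are 13, 38, 63 and 88, and their upper edges are 25, 50, 75 and 100. Moving from midpoint to upper edge shifts every scarred segment by 12 points, far more than the biases above. The mean difference for visual v quantitative would then depend heavily on a choice that the plan does not state.

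**Unit of analysis.** If pairs are segments, section 4.2 leaves 16 per patient, so there could be up to 491 × 16 = 7,856 correlated pairs. Section 8.4 allows for repeated measures within a patient. Section 8.3 does not mention them.

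**The case against.** Section 8.3 says only that scar extent will be compared. It does not mention agreement, sets no pass or fail rule, and no later analysis depends on its result. For the narrower question of whether one method reads more scar on average, a paired test is valid. The study objectives concern prediction of treatment effect and recovery, and the ROC comparison of FWHM and 5SD in section 8.4 speaks to that more directly. All of this stands. It means that agreement statistics are an addition to the section and that the paired test need not be removed. It does not supply the missing information: the ROC comparison shows which method predicts recovery better, not how closely the two measurements match.

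A reader might infer that methods differing by ±20 points will generally pass and that close methods will generally fail. The figures do not support this. A bias of 2 points with SD 10.2 is significant 99% of the time at 491 pairs, and close methods without bias are significant only 5% of the time. The ±20 is an illustration and is not in the documents.

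A reader might also infer that the plan treats the methods as interchangeable, or would read a non-significant p that way. The documents do not say so. FWHM and 5SD are ranked as primary and exploratory, section 5.2 fixes visual transmurality for core-laboratory viability, and section 8.4 names transmurality and burden as alternatives. Misreading the p-value is a risk and not a stated intention.

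The ordinal-scale point is limited too. Section 5.2 describes segmental grades, and section 8.3 does not say that grades are subtracted from percentages. The pairing is unspecified, not shown to be wrong.

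**Conclusion.** The point holds in a limited form. The only analysis that section 8.3 fixes for comparing the methods addresses average difference, and it can rank two situations opposite to their individual agreement. Limits of about ±20 with no bias give 5% significance at any n. Limits of −3.4 to +4.4 with a half-point bias give 70% at 100 pairs and over 99% at 491. These figures rest on assumed biases, SDs and alpha and on independent patient-level pairs, with 491 as a ceiling. The Wilcoxon alternative has the same limitation.

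The consequence is small. This is one secondary analysis in an appendix. It cannot affect the trial's primary outcome, and no other analysis in the Viability Study SAP is made conditional on it.

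**What to change.** Amend Viability Study SAP section 8.3 as follows:

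1. Keep the paired t-test or signed-rank test, described as a test of average bias between methods.
2. For FWHM v 5SD, add the Bland-Altman mean bias with 95% limits of agreement, and an intraclass correlation.
3. For visual v quantitative, place the quantitative segmental value in the same five grades as section 5.2 and report a weighted kappa with a patient-clustered confidence interval.
4. State the unit of analysis (patient or segment) for each comparison. If visual grades are also turned into numbers for the paired test, state how.

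The cost is a few sentences of SAP text and slightly more analysis on data already planned for collection. Banding the quantitative value loses some information, but only for the kappa.

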8.4. Segmental LV function

Improvement in segmental function will be defined as an improvement in wall motion score ≥1 grade at follow-up. The frequency of functional recovery will be compared between segments based on scar transmurality/scar burden across time points using a repeated measures ANOVA to adjust for repeated measures within the same patient and over three time points of baseline, six months and one year. An unadjusted Cox regression model will be used to test for an interaction between scar transmurality/scar burden and the provision of revascularisation and the likelihood of functional recovery, adjusted for baseline segmental wall motion. Two models will be used for revascularisation; the first where all segments will be considered revascularised in patients who were assigned to PCI, the second where only segments where a territory was documented as having been successfully revascularised in the eCRF, with the attribution of segments based on the standard American Heart

^{*}indexed to body surface area

Association 17-segment model adjusted for dominance of the circumflex or right coronary artery ⁹. Equivalent analyses will also be performed with scar transmurality/scar burden substituted for end diastolic wall thickness/end systolic wall thickness, as well as for different thresholds of LGE for viability (≤50% and ≤ 75%) and where scar burden is treated as a continuous variable. Receiver-operator characteristic curve analysis will be used to examine diagnostic utility, with Youden's index used to calculate the LGE threshold for optimum sensitivity and specificity to predict functional recovery. DeLong's method will be used to compare ROC curves for the prediction of recovery between the FWHM and 5SD methods of defining regions of myocardial scar.

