5.1. Wall motion scoring

For CMR and DSE, wall motion score will be classified on a five-point ordinal Likert scale as 1 – normal, 2 – hypokinetic, 3 – akinetic, 4 – dyskinetic, 5 – aneurysmal. For GSTT echocardiography core laboratory (non-DSE) measurements, the latter two points are combined into one category.

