8.5. Regional LV function

Improvement in regional function will be defined as an improvement in mean wall motion score index ≥ 0.5 across a coronary vascular territory, and by improvement in wall motion score index ≥ the median change. Vascular territories will be defined according to the AHA 17 segment model⁹. The frequency of functional recovery will be compared between territories which were and were not revascularised based upon scar burden, median wall thickness and the proportion of viable segments or ischaemic segments within the subtended territory. A Cox regression analysis will be used to determine the factors best predictive of functional recovery. The analysis will be conducted in three cohorts; the first within the whole trial population, the second solely within those assigned to receive PCI, and the third in all those vascular territories which met trial-defined criteria for viability (median scar burden ≤ 25%).

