The extent of inducible ischaemia will be determined on a per-patient basis. Ischaemic burden will be compared with myocardial jeopardy by converting both values to percentages of total LV volume (assuming a jeopardy score of 12 = 100% ischaemic burden. Kaplan-Meier plots for the primary outcome will be constructed based upon the presence/absence of significant inducible ischaemia (at least 1 segment of transmural ischaemia or 2 subendocardial segments in the same coronary territory) and based on the presence of ischaemia in >1 coronary vascular territory and separated by treatment assignment. A Cox regression model will be used to determine the effect of ischaemic burden on the primary outcome, key secondary outcomes and on global functional recovery, adjusted for treatment assignment and other key prognostic variables. A repeated measures ANOVA will compare the likelihood of functional recovery between segments with and without ischaemia, accounting for repeated measures in the same patient. A Cox regression model will be used to test for interaction between the presence of inducible ischaemia and segmental functional recovery, adjusted for segmental scar transmurality, wall thickness and revascularisation status. Further analyses will be performed where segmental ischaemia is defined as either a visible perfusion defect or a dysfunctional and viable segment¹⁵.

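### The Viability Study SAP's segmental recovery analyses do not exclude segments that are normal at rest and cannot improve, and one ischaemia definition in 8.7 is linked to recovery by construction

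*Protocol*

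**What the plan says.** All references are to the Viability Study SAP unless stated.

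- **Scale (5.1).** Wall motion is graded "1 – normal, 2 – hypokinetic, 3 – akinetic, 4 – dyskinetic, 5 – aneurysmal".
- **Segmental outcome (8.4).** "Improvement in segmental function will be defined as an improvement in wall motion score ≥1 grade at follow-up".
- **Segmental comparison (8.4).** "The frequency of functional recovery will be compared between segments based on scar transmurality/scar burden across time points", by repeated measures ANOVA. Then: "Receiver-operator characteristic curve analysis will be used to examine diagnostic utility", with Youden's index giving the LGE threshold and DeLong's method comparing two ways of defining scar. None of these carries a condition on resting function.
- **Interaction model (8.4).** The Cox model concerns the "likelihood of functional recovery, adjusted for baseline segmental wall motion", although the same sentence opens by calling the model unadjusted.
- **Viability (5.2).** The core laboratory counts a segment as viable at 25% transmurality or less only "in a segment which is dysfunctional at rest". Main protocol section 11 likewise treats grades 2 to 5 as dysfunctional and requires viability in dysfunctional segments.
- **Territories (8.5).** Recovery is defined in two ways: a gain of at least 0.5 in mean wall motion score index, and a gain of at least the median change. The third cohort is the territories "which met trial-defined criteria for viability (median scar burden ≤ 25"%.
- **Ischaemia (8.7).** After the perfusion-defect analyses, further ones are planned "where segmental ischaemia is defined as either a visible perfusion defect or a dysfunctional and viable segment". The segmental Cox model adjusts for scar, wall thickness and revascularisation, not baseline wall motion.

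**The concern.** A segment at grade 1 counts as not recovered whatever happens to it. If such segments carry little scar, they add certain failures to the low-scar bands. That lowers the apparent recovery rate where scar is least, pulls the AUC towards 0.5 and can move the Youden cut-point. That cut-point is a planned result of 8.4: the LGE threshold offered as optimal for predicting recovery.

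In 8.5 a territory whose mean index is below 1.5 fails the 0.5 rule automatically. The third cohort is labelled with the trial's viability criterion but states only its scar half, so normal territories can enter it.

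In 8.7 the further definition makes resting dysfunction part of the exposure. Normal segments without a perfusion defect all fall into the comparator, where they cannot recover, so an association appears even if ischaemia has no effect.

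**Working it through.** The plan gives no figure for these analyses, so there is none to reproduce. The floors are arithmetic; the sizes below are illustrations.

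**Floors.** Best possible change for a segment = baseline grade − 1, which is 0 at grade 1. For a territory it is baseline mean − 1, which is below 0.5 when the mean is below 1.5. Example: five segments, two hypokinetic, mean (3×1 + 2×2)/5 = 1.4. If both normalise, the gain is 0.4 and the 0.5 rule is still failed.

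**Assumed inputs (not in the documents).** Over the five scar bands of section 5.2:
- dysfunctional segments 30/20/20/15/15%;
- normal segments 70/20/7/2/1%;
- recovery in dysfunctional segments 60/50/35/15/5% (moderate), 80/60/40/10/2% (steep) or 50/45/40/30/25% (weak);
- f = share of segments normal at rest.

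**AUC.** With r_i and n_i the recovered and non-recovered shares in band i, and R and N their totals, AUC = Σ r_i (Σ_{j>i} n_j + n_i/2) / (R × N).

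*Moderate, f = 0.* r = 0.18, 0.10, 0.07, 0.0225, 0.0075 (R = 0.38); n = 0.12, 0.10, 0.13, 0.1275, 0.1425 (N = 0.62). AUC = 0.1744/0.2356 = 0.74.

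*Moderate, f = 0.3.* r = 0.126, 0.07, 0.049, 0.01575, 0.00525 (R = 0.266); n = 0.294, 0.13, 0.112, 0.09525, 0.10275 (N = 0.734). AUC = 0.1153/0.1952 = 0.59. Recovery in the 0% scar band falls from 60% to 0.126/0.42 = 30%, below the 1–25% band at 0.07/0.20 = 35%, so the gradient reverses there.

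| f | Moderate | Steep | Weak | Moderate, normal segments with same scar profile |
|---|---|---|---|---|
| 0 | 0.74 | 0.83 | 0.61 | 0.74 |
| 10% | 0.69 | 0.76 | 0.56 | 0.73 |
| 20% | 0.64 | 0.70 | 0.52 | 0.71 |
| 30% | 0.59 | 0.64 | 0.48 | 0.70 |
| 40% | 0.55 | 0.60 | 0.45 | 0.69 |

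**Youden cut, moderate.** At f = 0, ≤25% scar gives 0.28/0.38 + 0.40/0.62 − 1 = 0.38, against 0.35/0.38 + 0.27/0.62 − 1 = 0.36 for ≤50%. At f = 20%, ≤25% gives 0.737 + 0.489 − 1 = 0.23 and ≤50% gives 0.921 + 0.319 − 1 = 0.24, so the chosen threshold moves to ≤50%. It also moves at 20% in the steep case and at 10% in the weak case. It does not move if normal segments share the dysfunctional scar profile.

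**8.4 Cox model.** In a simulation at f = 40%, the rate ratio per scar category was 0.85 without baseline wall motion, 0.71 with it linear and 0.64 with it categorical. The value without normal segments is 0.64.

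**8.7, further definition, no true effect.** Assume 35% recovery in every dysfunctional segment and perfusion defects in 20% of all segments regardless of resting function; half of the dysfunctional segments have ≤25% scar. At f = 30%:
- ischaemic: 0.35 + 0.07 dysfunctional and 0.06 normal = 0.48; recovery 0.35 × 0.42/0.48 = 31%;
- non-ischaemic: 0.28 dysfunctional and 0.24 normal = 0.52; recovery 0.35 × 0.28/0.52 = 19%.

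The risk ratio is 1.62. At f = 10, 20 and 40% it is 1.18, 1.38 and 1.91; at f = 0 it is 1.00. Adjusting for scar does not remove this: among segments with ≤25% scar, every non-ischaemic one is normal, so recovery there is exactly zero. The perfusion-defect definition gives 1.00 at every f under the same assumptions.

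**The case against.** **The restriction may be implied.** The SAP's background and section 5 tie viability to dysfunctional myocardium, 8.4 speaks of thresholds for viability, and the parenthesis in 8.5 could be shorthand for the scar component. This is the strongest defence, but it does not settle the matter. Sections 7.1 and 7.2 include normal segments only in a labelled sensitivity analysis, so the authors mark the distinction when they intend it. Section 8.2 lists the number of segments with normal function as a variable, so such segments are expected. Section 8.4 compares segments by scar, not viable segments. An analyst following the text would keep them.

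**Stronger readings that the documents do not support:**
- That every recovery analysis is compromised. The 8.4 Cox model adjusts for baseline wall motion and is largely protected if that enters as a category, partly if linearly.
- That ischaemia in general is predictive by construction. This holds only for the further definition in 8.7.
- That all territories below 1.5 should be dropped from 8.5. A territory at 1.4 can gain 0.3 and may satisfy the median-change definition.
- That section 9.3 shares the fault. It plans a paired t-test of segmental change, not the binary outcome.

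**The sizes rest on assumptions.** This stands. Neither the share of normal segments nor their scar profile is given. The 8.7 result also depends on how often normal segments have perfusion defects. Take 30% recovery in dysfunctional segments, 60% of them called ischaemic, and 30% normal segments. With no defects in normal segments the contrast is 30% against 0.084/0.58 = 14%; with defects in 30% of them it is 0.126/0.51 = 25% against 0.084/0.49 = 17%.

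**Conclusion.** The point holds for four items: the 8.4 recovery frequencies and ROC/Youden/DeLong analyses, the 0.5 rule in 8.5, the third cohort in 8.5, and the further ischaemia definition in 8.7. That grade 1 segments and territories below 1.5 cannot meet the stated outcomes needs no assumption. The damage to scar discrimination does: with mostly scar-free normal segments making up 10 to 40% of the total, the moderate-case AUC falls from 0.74 to between 0.69 and 0.55, and the threshold can shift from 25% to 50%. With equal scar profiles the loss is small and the threshold stays. No size was worked out for the DeLong comparison itself. For the further 8.7 definition, a spurious ratio of about 1.2 to 1.9 arises over the same range. All of this concerns the secondary CMR appendix. Neither the trial's primary analysis nor the main viability analyses in 7.1 to 7.3 are affected.

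**What to change.** 1. **8.4 and 8.7:** restrict the segmental recovery analyses to segments with baseline grade 2 or worse, on the same reading from which improvement is counted. In the 8.4 Cox model, enter baseline wall motion as a category and remove the conflicting word unadjusted.
2. **8.5:** define the third cohort as dysfunctional at rest and scar of 25% or less, and say how a territory qualifies as dysfunctional. Apply a baseline mean index of at least 1.5 to the 0.5 definition only. For the median-change definition, exclude only territories with entirely normal resting function.
3. **8.7, further definition:** keep the scar adjustment after the restriction, because every remaining non-ischaemic segment then has more than 25% scar. With the moderate recovery rates and no ischaemia effect, an unadjusted comparison would still show (0.28 + 0.02)/0.60 = 50% against 0.08/0.40 = 20%.
4. **9.3:** no change on this ground.

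The cost is SAP wording and a filter on data already read. There will be fewer segments and territories, but those removed cannot improve by the amount that the outcome requires.
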